### **9.2.2.11 Pharmacodynamic (PD) assessment(s): QRS and other 12-lead ECG parameters over time**

PD results will be reported for the safety, PK and mITT populations. Section 6.2.5.2 indicates the planned time points PD information is measured. Information is provided by the Core Laboratory performing the analysis by extracting 12-lead ECGs from the AECG (Holter) recording at pre-defined time points.

For each time point triplicate measurements take place, the second and third measurements are planned at approximately 30 seconds and approximately 60 seconds after the initial measurement, respectively. Per subject per time point the mean value is calculated for the ECG parameters; these

---

## FLE-002 (INSTANT) – Final Analysis

## Statistical Analysis Plan

---

mean values are used in all PD analyses.

The following parameters will be reported:

- Heart Rate (bpm)
- QRS Interval Duration (msec)
- QTc Interval Duration (msec)
- JTc Interval Duration (msec)
- RR Interval Duration (msec)
- PR Interval Duration (msec)

*PR is only available if subject is in SR*

Baseline Values will be summarized as Baseline (seated) and Baseline (semi-recumbent) (refer to SAP Section 3.5).

This information is reported per cohort per time period:

- a per subject listing of all PD values
- a per subject listing of the change of PD values compared to baseline value (seated) (delta).

For ΔQRS interval (msec) additionally the maximum is shown.

- a per cohort table of mean and standard deviation of PD values
- a per cohort table of mean and standard deviation of change of PD values compared to baseline values (seated) (delta).

For ΔQRS interval (msec) additionally the maximum is shown.

- a per cohort figure of ΔQRS interval (msec) and its standard error of mean.

Tables and figures can be repeated for specific reasons why subject Converted to SR (refer to SAP section 3.1, “definition of methods for cardioversion”), these additional analyses will be specified in the overview of TFLs that will accompany the final report.

PD results are reported for the Safety and the PK population.

Results for the Part C PLS study are available for 3 subjects only; results will only be listed, not tabulated.

### **9.2.2.12 Secondary safety endpoint (MLS)**

The secondary safety endpoint, the incidence of treatment emergent serious adverse events of special interest for flecainide (SAESI, refer to section 3.4 SAP for definition) is reported by analyzing AEs that fulfill all of these conditions:

- Events starts between initiation of inhalation of study drug and Visit 2.
- AE is a SAESI according to sponsor provided information (refer to SAP section Annex A).

Results will be reported for the Safety Population, meaning all subjects who started inhalation of study medication.

The MLS statistical report will summarize results as:

- total number of serious AESI and mean number of serious AESI per subject

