Doses of 30 mg (1 x 30 mg), 60 mg (2 x 30 mg), and 90 mg (2 x 45 mg) and 120 mg (2 x 60 mg) have been under evaluation in this study based on PK and PD data (QRS prolongation) from FLE-001 and FLE-003 showing that doses \geq 30 mg had the potential to convert AF to SR. Part A concluded after enrolling 101 subjects, as follows: 10 subjects treated with 30 mg eTLD, 22 subjects treated with 60 mg eTLD, 21 subjects treated with 90 mg eTLD, and 48 subjects treated with 120 mg (19 with FlecIH-102 and 29 with FlecIH-103. Enrollment in the 120 mg dose cohort was completed on 05Mar2020 and Part A was concluded. The rate of conversion from AF to SR observed to date for the dose cohorts is as follows: 30 mg, 1/10 (10%); 60 mg, 6/18 (33%; 2 subjects were excluded from analysis as they were not in AF at time of dosing); and 90 mg, 7/21 (33%); For the 120 mg dose, the conversion rate was 7/17 (41%) for the FlecIH-102 cohort (2 subjects were excluded from efficacy analysis because they did not receive the full dose of study drug) and 13/27 (48%) for the FlecIH-103 cohort (2 subjects were excluded from the efficacy analysis because they did not receive the full dose of study drug).

The majority of subjects had AEs that were mild in severity and the most commonly reported AEs were those associated with the inhalation route of administration, e.g., cough and throat irritation. All non-serious AEs of bradycardia and hypotension were minor, transient and resolved without drug treatment. A total of four subjects experienced serious AEs (SAEs) that were considered possibly related to study drug by the Investigator or Sponsor. The SAEs considered related to inhaled flecainide included the following: two cases of prolonged sinus pauses at the time of conversion of AF to SR (one mild and one moderate, as per the Investigators), one case of bradycardia (severe, as per the Investigator), and one case of atrial flutter with 1:1 conduction with fast ventricular response (severe, as per the Investigator). All SAEs were transient in nature, resolved without intervention, and had no sequelae.

Based on the feasibility, safety, tolerability and efficacy results from Part A using the FlecIH-103 inhalation solution, Part B and Part C of the study will use the 120 mg dose of flecainide to further evaluate the cardioversion of recent onset AF.

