7.5.2 B - Secondary endpoints

The secondary efficacy endpoints are:

The proportion of subjects with C_{max} values ≥ 200 ng/mL (e.g., 200, 300, 400, and 500 ng/mL) post inhalation with inhaled flecainide (excluding plasma levels associated with IV flecainide infusion) whose AF converted to SR by inhaled flecainide within 90 minutes after initiation of dosing.

Study no. FLE-002

Version 8.0 EU-1 Page: 63 of 117

- The time to conversion of AF to SR from initiation of dosing up to 90 minutes after initiation of dosing;
- The proportion of subjects in SR on Day 2;
- The proportion of subjects with reduced or no AF symptoms at 30 minutes post dose;
- The proportion of subjects with reduced or no AF symptoms at 60 minutes post dose;
- The proportion of subjects with reduced or no AF symptoms at 90 minutes post dose;
- The proportion of subjects who had their AF converted to SR within 90 minutes after initiation of dosing and had no AF recurrence requiring electrical or pharmacological cardioversion or rate control intervention, up to discharge;
- The proportion of subjects in SR on Day 5.

Time to conversion will be reported in statistical analyses from both initiation of study drug and completion of study drug.

The secondary safety endpoint is the incidence of treatment emergent serious adverse events of interest for flecainide

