8.0 EU-1 Page: 68 of 117 Version

9.1.2.4 B – Serious Adverse Events of Special Interest (SAESI)

The following potential SAESIs are defined for study purposes:

- Hypotension, with symptoms/signs of clinical instability (i.e., severe chest pain/dyspnea or altered mental status), and requiring a vasopressor or inotropic agent
- Ventricular tachycardia, sustained (> 30 seconds or requiring intervention before that time) VT, TdP, or VF
- Bradycardia, with symptoms/signs of clinical instability (i.e., severe chest pain/dyspnea, altered mental status or hypotension), and requiring pacing or a chronotropic agent
- Sinus pauses post conversion of AF to SR, causing syncope, or requiring pacing or CPR
- Atrial flutter with 1:1 conduction with fast ventricular response (ventricular heart rate ≥ 200 bpm), and requiring intervention (DC cardioversion) for termination, or an IV AV nodal blocking agent (β-blocker or Ca2+-channel blocker) to slow the ventricular rate
- Any arrhythmia with symptoms/signs of clinical instability (i.e., severe chest pain/dyspnea, altered mental status or hypotension), and requiring DC cardioversion, defibrillation, pacing, or a vasopressor, inotropic or chronotropic agent

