### 4. Definitions

- 4.1 Adverse Event (AE): Any untoward medical occurrence in a clinical investigation subject administered a pharmaceutical product and which does not necessarily have to have a causal relationship with this treatment.
- 4.2 AE of Special Interest (AESI): Any AE related to the inhalation device, any pregnancy that started while participating to the study, and AEs known to be related to other formulations of flecainide (i.e., IV and oral).
- 4.3 Non-Cardiovascular Adverse Event of Special Interest (Non-CV AESI): A subset of AEs coded in MedDRA within a System Organ Class (SOC) other than “Cardiac disorders” or “Vascular disorders, which includes AEs related to the inhalation device and any pregnancy that started while participating to the study as defined below:
  - Pregnancy: Any female study subject or female partner of a study subject that becomes pregnant while participating in this study
  - AE related to the inhalation device (nebulizer): AE considered directly related to the nebulizer
- 4.4 Serious Non-Cardiovascular Adverse Event of Special Interest: Non-CV AESI is considered serious if it meets the following criteria.
  - Pregnancy: Any female study subject or female partner of a study subject that becomes pregnant while participating in this study
  - AE related to the inhalation device: AE considered directly related to the nebulizer by the Investigator that meets the definition for a SAE
- 4.5 Cardiovascular Adverse Event of Special Interest (CV AESI): A subset of AEs coded in MedDRA within a System Organ Class (SOC) of “Cardiac disorders” or “Vascular disorders, which include AEs known to be related to flecainide as defined below.

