**FLE-002 (INSTANT) – Final Analysis****Statistical Analysis Plan**

- Hypotension: an acute hypotensive episode (AHE) is a sudden drop in BP resulting in a BP < 90/60 mmHg (MAP < 70 mmHg) that lasts for at least 5 minutes and is based on multiple sequential readings ( $\geq 3$ ). MAP is calculated as  $1/3$  (SBP – DBP) + DBP
- Ventricular Tachycardia (VT): Ventricular tachycardia (i.e., an ECG-derived rate  $>100$  bpm)  $> 3$  beats (excludes triplets)
- Bradycardia: an ECG-derived rate  $< 50$  bpm for  $\geq 1$  minute
- Sinus pause post conversion of AF to SR: an ECG-derived pause  $> 3$  seconds
- Atrial flutter with 1:1 conduction with fast ventricular response: Atrial flutter with a ventricular heart rate  $\geq 200$  bpm

4.6 Serious Cardiovascular Adverse Event of Special Interest: A CV AESI is considered serious as defined below.

[figure not shown]
- Hypotension per AESI definition in Section 4.5 with symptoms/signs of clinical instability (i.e., severe chest pain/dyspnea or altered mental status) and requiring a vasopressor or inotropic agent
- Ventricular tachycardia per AESI definition in Section 4.5 that is sustained ( $> 30$  seconds or requiring intervention before that time) VT, TdP, or VF
- Bradycardia per AESI definition in Section 4.5 with symptoms/signs of clinical instability (i.e., severe chest pain/dyspnea, altered mental status or hypotension) and requiring pacing or a chronotropic agent
- Sinus pauses post conversion of AF to SR per AESI definition in Section 4.5, causing syncope or requiring pacing or CPR
- Atrial flutter with 1:1 conduction with fast ventricular response per AESI definition in Section 4.5, and requiring intervention (DC cardioversion) for termination or an IV AV nodal blocking agent ( $\beta$ -blocker or Ca2+-channel blocker) to slow the ventricular rate

Any arrhythmia with symptoms/signs of clinical instability (i.e., severe chest pain/dyspnea, altered mental status or hypotension), and requiring DC cardioversion, defibrillation, pacing, or a vasopressor, inotropic or chronotropic agent. Serious AESIs in this category will also be included in the broader category of CV AESI described in Section 4.5.

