## FLE-002 (INSTANT) – Final Analysis

## Statistical Analysis Plan

---

5.2.2 Each AE will be reviewed, and documented as follows:

- AE type (select only one option)
  - Non-AESI (standard AE)
  - Non-CV Non-Serious AESI
  - Serious Non-CV AESI
  - CV Non-Serious AESI
  - Serious CV AESI
- Initials
- Date
- Comment

5.2.3 The Reviewer initials and dates next to each recoded item and provides comments as necessary.

5.2.4 The Reviewer also signs a memorandum to record execution.

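### For cardiovascular events, the secondary safety endpoint judges seriousness by SAESI criteria that mostly require intervention and not by the SAE criteria, so a flecainide AESI that was an SAE but resolved untreated can be coded non-serious and left out of the count

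*SAP*

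**What the plan says.** Protocol 7.5.2 B states: "The secondary safety endpoint is the incidence of treatment emergent serious adverse events of interest for flecainide". Protocol 17.2.2.1 sends the seriousness judgement for each AE to Section 17.2. The criteria in 17.2.1.2 are death, threat to life, hospital admission (with stated exceptions), disability, congenital anomaly and other medically important conditions. An event can meet them without having been treated.

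Protocol 9.1.2.4 B separately lists serious adverse events of special interest (SAESIs). Its bradycardia entry reads "Bradycardia, with symptoms/signs of clinical instability (i.e., severe chest pain/dyspnea, altered mental status or hypotension), and requiring pacing or a chronotropic agent".

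SAP 6.2.3 reads the endpoint as the incidence of SAESIs. SAP 9.2.2.12 counts an event that starts between first inhalation and Visit 2, provided that "AE is a SAESI according to sponsor provided information (refer to SAP section Annex A". Annex A 4.6 says "A CV AESI is considered serious as defined below" and then gives essentially the protocol's list, tied to the AESI thresholds of Annex A 4.5. The bradycardia entry again ends "altered mental status or hypotension) and requiring pacing or a chronotropic agent".

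For device events, Annex A 4.4 takes a different basis: "AE considered directly related to the nebulizer by the Investigator that meets the definition for a SAE". Any pregnancy counts as serious.

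Annex A 5.2.2 allows one code per event, from five options. A cardiovascular AESI that fails the 4.6 list becomes "CV Non-Serious AESI".

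**The concern.** Two standards of seriousness run side by side without being linked. The SAE tables use the six EDC questions described in SAP 5.6.1. The endpoint uses the Annex A list. The same bradycardia could be an SAE in one table and sit under a non-serious label in another. Within Annex A, device events are tested against the SAE definition and the flecainide-type cardiac events are not.

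This is the only secondary safety endpoint, in an open-label study of a drug with proarrhythmic risk. Event types already reported as related SAEs in Part A can be absent from it. The SAE and TESAE tables are by system organ class and preferred term, and the AESI table is by AESI type. No planned table shows which AESIs were SAEs, and SAE status is not among the listing flags named in SAP 9.2.2.9. A reader who relies on the endpoint row would not see these events as serious.

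**Working it through.** **Inputs**
- Part A related SAEs (protocol 1.4): two prolonged sinus pauses at conversion, one severe bradycardia and one severe 1:1 flutter. Check: 2 + 1 + 1 = 4, the stated number of subjects.
- Outcome (protocol 1.4): "All SAEs were transient in nature, resolved without intervention, and had no sequelae".
- Part A treated subjects, all doses: 10 + 22 + 21 + 48 = 101, as stated.
- Part A subjects who enter the final analysis: 29 on 120 mg FlecIH-103 (protocol 1.4; SAP 8.7.2).

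**Step 1: what Annex A 4.6 needs for a cardiovascular AESI to be serious**
- Hypotension: clinical instability and a vasopressor or inotrope.
- Bradycardia: clinical instability and pacing or a chronotropic drug.
- 1:1 flutter: cardioversion, or an IV nodal blocker to slow the rate.
- Any arrhythmia: clinical instability and one of the listed interventions.
- Ventricular tachycardia: over 30 seconds or earlier intervention; TdP or VF also qualifies. Intervention is not necessary.
- Sinus pause after conversion: syncope, pacing or CPR. Syncope alone is enough.

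Four of the six entries cannot be met without intervention. None refers to the SAE criteria.

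**Step 2: the four Part A events against this list**
- Bradycardia: no intervention, so it cannot be a SAESI.
- 1:1 flutter: no intervention, so it cannot be a SAESI.
- Two pauses: no intervention, so each qualifies only if it caused syncope. The documents do not say.

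The list therefore captures 0 to 2 of the four. Two are certainly excluded. Two to four would be coded as non-serious AESIs if they meet the AESI thresholds.

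**Step 3: rates, x/n with exact (Clopper-Pearson) 95% intervals**
- SAE basis, all Part A doses: 4/101 = 4.0% (1.1-9.8%).
- SAESI basis, both pauses with syncope: 2/101 = 2.0% (0.2-7.0%).
- SAESI basis, neither pause with syncope: 0/101 = 0% (0-3.6%).
- SAE basis among the 29 FlecIH-103 subjects, where the number of these SAEs is not given: from 0/29 = 0% (0-11.9%) to 4/29 = 13.8% (3.9-31.7%).

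The 101-subject figures illustrate the effect of the definition. They are not a forecast of a table in the final report, which pools only 120 mg FlecIH-103 subjects.

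**The case against.** **The definition is the protocol's.** Protocol 9.1.2.4 B defines SAESIs for study purposes, and the protocol names serious AEs and serious AESIs separately in the Part C eligibility rule. Reading the endpoint as the SAESI count is reasonable. This stands: the SAP has not departed from the protocol here, and the tension between 9.1.2.4 B and 17.2.2.1 lies in the protocol and is inherited. It is also a reason to keep the SAESI count.

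**The events are not lost.** SAP 9.2.2.9 tabulates SAEs and TESAEs by cohort and AESIs by type, and lists investigator or CRO classifications beside the sponsor's. This stands too. It limits the harm to the endpoint row and the label, but it leaves the same event serious in one table and non-serious in another.

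**Sponsor review has a reason.** AESI definitions changed between protocol versions and SAESI status was not collected before version 8.0. A second person verifies the assessments (Annex A 5.3). This supports uniform sponsor coding of SAESI status. It is no reason to leave SAE status, which is already recorded, out of the display.

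**The stakes are limited.** No formal testing is planned and no decision rule uses this count. That is fair, and the change asked for is correspondingly small.

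**Stronger readings that the documents do not support.** A reader might infer that an AESI counts only if it was treated. The tachycardia, TdP, VF and syncope routes show otherwise. A reader might infer that all four Part A SAEs drop out. Only two certainly do. SAESI was first defined in version 8.0 (February 2021), after Part A closed in March 2020, so a reader might also infer that the list was drawn to exclude those events. The documents do not say so. SAP 9.2.2.9 attributes the AESI changes to examination of the data and discussion with the regulator, and SAP 5.6.5 cites alignment with terms agreed for Phase 3.

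**Conclusion.** The point holds as a defect of definition and labelling in one endpoint. A hypotension, bradycardia or 1:1 flutter AESI that met the SAE criteria but resolved untreated cannot enter the secondary safety endpoint and is coded non-serious. The same holds for a pause without syncope. This follows from the text and needs no assumption about the data.

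The size is illustrative. On Part A's four related SAEs the endpoint rule gives 0-2.0% of 101, against 4.0% on the SAE basis. This assumes that each event meets its AESI threshold, since pause lengths, rates and durations are not given. The range of 0 to 2 reflects the unknown syncope status. The effect on the reported pooled cohort could be nil if none of the four was among the 29 FlecIH-103 subjects. The Annex A 4.7 decision tree survives only as two lines of text, so any further rule in that figure could not be checked.

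**What to change.** - In SAP 6.2.3 and 9.2.2.12, keep the SAESI count as defined. Add a row beside it for treatment-emergent flecainide AESIs that meet the SAE criteria of protocol 17.2.1.2, with events, subjects and percentage by cohort.
- Take SAE status from where it is already held: the EDC for Parts B and C, and the safety database for Part A.
- In SAP 5.6.5 and Annex A 5.2.2, record SAE status and SAESI status as two separate fields.
- Rename the non-serious AESI categories as AESIs not meeting SAESI criteria.

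The cost is SAP and Annex A wording and one table row, with no new data collection and no change to a clinical rule. The added row may show a less favourable rate than the SAESI count alone.

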**FLE-002 (INSTANT) – Final Analysis****Statistical Analysis Plan**

-total number of subjects with at least one serious AESI, percentage of subjects with at least one serious AESI

Additionally details of the Serious AESI will be shown in the listings in the statistical report.

Serious AESIs (SAESI) will be reported as follows:

- 1) All SAESIs from time of MLS consent through MLS End of Study (EoS)
- 2) MLS Treatment Emergent SAESIs from start of MLS dosing through MLS Day 5

**9.2.2.13 Safety endpoint (PLS)**

The secondary safety endpoint, the incidence of treatment emergent serious adverse events of special interest for flecainide (Serious AESI, refer to section 3.4 SAP for definition) is defined as follows:

- Adverse Events starts between initiation of PLS study drug and PLS Day 5 *and*
- AE is a SAESI according to sponsor provided information (refer to SAP section Annex A).

AEs reported from the time of PLS consent until the initiation of PLS study drug are thus not considered treatment emergent.

Endpoints will not be reported in statistical tables, but a listing will include all information required to derive endpoint. Refer to section 9.2.2.9 SAP for the information included in the listing.

Adverse events will be reported as follows:

- 1) PLS Treatment Emergent AEs from the initiation of PLS study drug through PLS Day 5 (End of Study)
- 2) All AEs from time of PLS consent through PLS End of Study

**9.2.3 Additional Analyses****9.2.3.1 Vital Signs**

The investigator reported values from vital sign measurements (heart rate, respiration rate, etc.) will be used. Vital sign values after initiation of inhalation will be compared with the semi-recumbent Baseline value at 30 minutes pre-initiation to study medication, in case this value is missing the semi-recumbent Baseline value at 45 minutes pre-initiation will be used. In case also the 45 minutes pre-initiation value is missing, the Baseless value nearest to initiation of study medication will be used as reference value.

For the MLS part of the study a table will report baseline values, a second table will report the post initiation results and the change compared to baseline.

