8.0 EU-1 Page: 33 of 117 Version

concentration vs time for the IV dose was normalized to 30 mg in order to match the 30 mg oral inhalation dose (Figure 2). The resulting concentration-time profile curves are near-identical, indicating comparable pharmacokinetics by these two routes of administration. The results of the cross-over comparison between IV and inhaled flecainide also clearly demonstrated that the reported adverse events were far fewer and less intense following inhalation of a lower dose of flecainide (30 mg eTLD) than the 10 min IV infusion of 2 mg/ml of flecainide.

Figure 2. Venous plasma concentration- time curve following flecainide IV (normalized to 30 mg dose) and oral IH

Values are mean ± SD. Inset shows the first 70 minutes after start of dosing. The Least Square Mean C_{max} value for the IV infusion was 143 ng/ml and that for the inhalation was 102 ng/ml. Note that the estimated bioavailability of flecainide given via IH is ≈75% compared to the 100% given via IV.

The changes in heart rate (HR), arterial systemic blood pressure (BP), and pulmonary function test parameters associated with administration of flecainide or placebo were assessed. Transient (5 to 10 mins) increases in both HR and systolic and diastolic BPs were noted in subjects that were given inhaled flecainide and placebo. These changes were not dosedependent, and are, in part, due to the sympathetic reflex responses associated with postural changes (from semi-recumbent to seated) and are also, likely, due to the oral inhalation procedure.

All standard lung spirometry measurements and peripheral oxygen saturations (pulse oximetry) values were normal before and after flecainide or placebo. No SAEs were reported and no subject had to interrupt the inhalation of flecainide acetate or placebo. The changes in vital signs (HR, BP, respiratory rate) and pulmonary function are described in detail in the IB (IB Section 5.2.1.2.3)⁴¹.

INSTANT Study Clinical Study Protocol

Study no. FLE-002

Version 8.0 EU-1 Page: 34 of 117

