5.3.4 B – Administration

Subjects will be dosed with 120 mg eTLD (2 x 60 mg) FlecIH-103 (75 mg/mL) inhalation solution: 2 inhalations of 3.5 minutes each, separated by a 1-minute break ('dose/inhale to conversion'). Dosing in a 'dose/inhale to conversion' regimen continues until the conversion of AF to SR is observed for \geq 1 minute, or until the full dose is completed, whichever comes first.

For the administration of study drug, the following procedures are to be performed:

Study no. FLE-002

Version 8.0 EU-1 Page: 49 of 117

1. The subject must be seated in an upright position in a chair or adjustable bed from approximately 30 minutes prior to the start of inhalation up to completion of dosing, at which point subjects may return to a semi-recumbent position. A height-adjustable table must be placed in front of the subject (e.g., overbed table on casters), whereby the subject can rest his/her arms during the inhalation regimen. The set up at the site will allow for subject to remain in this upright sitting position while connected to the cardiac monitoring system and while blood samples are collected during the self-administration of the inhalation solution.

NOTE: Subjects may be placed in a semi-recumbent, supine, or other position as needed for an adverse event, at the discretion of the investigator. These occurrences will not constitute a protocol deviation.

- 2. The subject is given instructions from study personnel on how to inhale the study drug according to the IFU.
- 3. The subject is required to use a nose clip to seal off their nostrils during inhalation, unless the subject refuses.
- 4. The subject may practice the inhalation procedure (without flecainide) prior to starting the inhalation of study drug.
- 5. The inhaler must be connected to medical compressed air that is set at a steady flow rate of 5 L/min.
- 6. The subject shall be informed prior to the start of the inhalation about the potential to experience throat discomfort, bad taste, and the impact of the sensation caused by the vapors being inhaled.
- 7. If not contraindicated, a topical oral anesthetic (e.g., containing lidocaine or phenol) spray (e.g., Medica, Chloraseptic) or lozenge (e.g., Trachitol, Cepacol) may be used by the subject to prophylactically mitigate the discomfort or pain associated with the inhalation and thereby improve the tolerability.
- 8. The subject inhales the study drug using a fully assembled AeroEclipse® II BAN provided by the study nurse.

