NOTE: For the medication to be effectively delivered into the lungs, the subject must be seated in an upright position;

NOTE: When subject changes their position from seated to semi-recumbent or vice versa, the subject must be allowed time to stabilize in the new position for about 10 minutes for PD assessments;

- Vital signs (heart rate, systolic and diastolic blood pressure, respiratory rate (breaths/min) and oxygen saturation) are collected from telemetry at 45 (semi-recumbent), 30 (semi-recumbent), and 15 (seated upright) minutes prior to the start of study drug.
 - For vital signs where 3 measurements are required during screening, at least 2 of the 3 assessments during screening must be within the eligibility requirements. Additionally, these criteria shall be rechecked at T₀ for confirmation of eligibility prior to dosing. If the T₀ assessment is not within eligibility requirements, subject is not eligible to receive the study drug and will be early terminated.

Triplicate 12-lead ECG readings are extracted from the AECG (12-lead Holter) recording by the ECG Core Laboratory for the 45-, 30-, and 15-minute pre-dose time points after receipt of the data.

Adverse events and concomitant medications are continually assessed and recorded from time of IC through EOS.

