### Baseline (seated)

The mean of all available Baseline Values at these time points: 15 minutes pre-initiation of study drug and just before initiation of study drug ( $T_0$ )

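### Vital-sign readings taken during seated dosing are compared with a semi-recumbent baseline, so posture and the change after dosing are mixed in an uncontrolled descriptive table

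*SAP*

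**What the plan says.** SAP 9.2.3.1 sets one reference rule for every vital sign recorded after inhalation starts: "Vital sign values after initiation of inhalation will be compared with the semi-recumbent Baseline value at 30 minutes pre-initiation to study medication". The first fallback is the -45 minute semi-recumbent value. The second is worded "the Baseless value nearest to initiation of study medication will be used as reference value" (presumably Baseline is meant). For the medically-led part, "a second table will report the post initiation results and the change compared to baseline".

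Protocol 6.1.3 B fixes the pre-dose postures: vital signs are taken "at 45 (semi-recumbent), 30 (semi-recumbent), and 15 (seated upright) minutes" before the start of study drug. Protocol 5.3.4 B then keeps the subject upright "up to completion of dosing, at which point subjects may return to a semi-recumbent position".

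The SAP defines a posture-matched alternative. Baseline (seated) in SAP 3.5 is "The mean of all available Baseline Values at these time points: 15 minutes pre-initiation of study drug and just before initiation of study drug". SAP 9.2.2.11 uses it for the ECG parameters, for example in "a per subject listing of the change of PD values compared to baseline value (seated) (delta". Heart rate is one of those parameters.

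Protocol 1.2.2 reports short-lived rises in heart rate and blood pressure in Phase 1, with placebo as well as flecainide, and judges them in part "due to the sympathetic reflex responses associated with postural changes (from semi-recumbent to seated". It names the inhalation procedure as a further likely cause.

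**The concern.** The reference is semi-recumbent, but some of the readings compared with it are seated. The protocol itself names this posture change as a partial cause of movements in heart rate and blood pressure. The SAP recognises the distinction by defining two baselines, yet for vital signs it applies the semi-recumbent one at every time point and gives no reason.

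In a controlled trial a common posture shift would largely cancel between arms. This trial is open-label with a single treatment (SAP 7.1.2), so nothing cancels it. Change from baseline over time is a planned safety summary (Protocol 10.2.2.2 B). The readings most exposed are those during and just after inhalation, when Protocol 1.2.2 expects drug to be reaching the circulation. What is at stake is how that table, and the time-course plot based on it, will be read.

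**Working it through.** The plan states no figure to reproduce, and the documents give no mmHg or bpm value for the posture difference. The check is to set the posture of each reading beside the posture of its reference.

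**Posture by time point** (Protocol 5.3.4 B, 6.1.3 B, 6.2.1 B, 6.3 B; Schedule of Assessments, Table 4)

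| Reading | Posture | Matches the -30 or -45 minute reference? |
|---|---|---|
| Break, 3.5 to 4.5 min after start | Seated | No |
| At SR, conversion during dosing | Seated | No |
| +1 and +3 min post dose | Still seated, or just returned to semi-recumbent | No, or not settled |
| +10 min | Not fixed | Borderline |
| +30, +60, +90 min | Not fixed | Only if the subject has lain back |
| At SR, conversion after dosing | Not fixed | Depends on posture |

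The seated entries follow the protocol rule. Protocol 5.3.4 B allows another position when an adverse event requires it. For +1 to +10 minutes, Protocol 6.1.3 B asks for about 10 minutes of settling after a posture change. It says so for the ECG assessments, but it is the only guide the documents offer.

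**What the change score contains.** Let D be the change after dosing at a fixed posture, and P the seated value minus the semi-recumbent value.

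- Seated reading against the semi-recumbent baseline: D + P
- Seated reading against Baseline (seated): D
- Semi-recumbent reading against the semi-recumbent baseline: D
- Semi-recumbent reading against Baseline (seated): D - P

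Neither baseline is right at every time point. The break reading carries the full P under the current rule.

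**What the trial can say about P.** Each subject has two readings in each posture before drug, so P can be estimated as mean(-15, T0) minus mean(-45, -30). The two seated values are collected but serve as a reference only when both semi-recumbent values are missing.

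**Timing since sitting up.** Protocol 6.1.3 B has the subject sit up about 15 minutes before inhalation. The regimen lasts 3.5 + 1 + 3.5 = 8 minutes.

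- Break: 15 + 3.5 = 18.5 to 15 + 4.5 = 19.5 minutes after sitting up
- +1 minute: 15 + 8 + 1 = 24 minutes
- +3 minutes: 15 + 8 + 3 = 26 minutes

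Protocol 5.3.4 B instead says about 30 minutes, which adds 15 to each figure. Either way these readings come later than the 5 to 10 minutes that Phase 1 gives for the transient rise, if that time is counted from sitting up.

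**Final fallback.** The value nearest initiation is normally T0, which is seated. A subject who reaches this step has a seated reference while others in the table have a semi-recumbent one. For systolic pressure and heart rate this should be rare, because exclusion criterion 2 needs two of the three screening readings (-45, -30, -15) within limits.

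**The case against.** The case for leaving the rule alone has real substance.

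- **Events of special interest.** A reader might infer that the mismatch hides hypotension or bradycardia events. It does not. Hypotension is defined by BP below 90/60 mmHg (MAP below 70) and bradycardia by a rate below 50 bpm (Protocol 9.1.2.3 B; SAP Annex A 4.5). These are absolute thresholds, and neither they nor the serious-event definitions built on them use the SAP 9.2.3.1 reference. This stands in full.
- **Heart rate.** ECG heart rate is already summarised as change from Baseline (seated) at the break and post-dose points. This stands, and leaves mainly blood pressure and the other site-recorded values.
- **Size and direction.** It is tempting to say that the 5 to 10 minute Phase 1 rise covers the break and the +1 and +3 minute readings, so that falls are masked. Subjects sit up well before dosing, so a short reflex may be over by then. A rise timed to dosing would fit the inhalation procedure better, and a seated baseline would not remove it. Only a sustained difference between postures would matter, and the documents give neither its size nor its sign.
- **Posture after dosing.** Return to semi-recumbent is optional, so a blanket switch to the seated baseline would create the reverse mismatch for those who lie back. The -15 minute reading may also fall close to the moment of sitting up.
- **Presentation.** The SAP says change compared to baseline, not drug effect. Post-initiation values appear beside the change, and all data are listed. The protocol fixes no posture for the baseline.

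These arguments limit the consequence but do not remove the mismatch. The break reading is seated by protocol and its reference is not.

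**Conclusion.** The mismatch is certain for the break reading and for at-SR readings during dosing, apart from subjects repositioned for an adverse event. At +1 and +3 minutes the reading is either seated or taken shortly after lying back. At these points the change-from-baseline table for the medically-led cohorts mixes P with the change after dosing, and no comparator separates them. The patient-led data are only listed.

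The size is unknown. If P is close to zero after 15 minutes or more of sitting, the correction changes little. If a sustained difference remains, the break change is off by that full amount.

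The documents do not support a stronger reading, namely that drug-induced hypotension or bradycardia will be missed, that the report labels a posture shift as drug effect, or that the Phase 1 transient fixes the direction of the bias. No endpoint or event count depends on the choice. The point is minor: a descriptive safety table with an avoidable ambiguity, mainly in blood pressure.

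The conclusion assumes that the -30 minute reading really is semi-recumbent, as Protocol 6.1.3 B and footnote 11 of Table 4 indicate. Protocol 5.3.4 B, with about 30 minutes of sitting, leaves that less clear.

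**What to change.** In SAP 9.2.3.1:

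- Reference the break reading, and at-SR readings during dosing, to Baseline (seated) as defined in SAP 3.5.
- At the post-dose time points, where posture is not fixed, show the change against both the seated and the semi-recumbent baseline.
- For the final fallback, state which posture the substitute value has and flag the subjects concerned, so that one column does not silently mix references. Correct the misprint in that sentence.

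Reporting the pre-dose difference, mean(-15, T0) minus mean(-45, -30), would show readers how much the choice matters. The two protocol statements on when the subject sits up should be reconciled. If posture was recorded at the post-dose readings, adding it to the listing would help.

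The cost is a short SAP edit, a second reference variable and one extra set of columns in a descriptive table. No new data are needed. A seated baseline will not remove any effect of the inhalation procedure itself, and a table footnote should say so.
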